9.1.2.3 Shipping of Specimens

Samples must be shipped from the site to the respective laboratory within 30 days of last sample collection in order to receive cost reimbursement. The sample collection and shipping dates must be documented in the eCRF.

- Please store serum samples for PK/ADA at -80°C until shipment and ship to PPD on dry ice using Federal Express as the courier.

PPD

[Redacted contact information for PPD]

- Include an electronic shipping manifest with each shipment.
- Notify PPD of all shipments via email and cc, [name], , and [name] at Apexigen on the day of shipment.

[contact]
- [contact]

[contact]
[contact]

9.1.2.4 Site Performing Correlative Study

Apexigen will have the PK and ADA analyses performed by the Pharmaceutical Product Development (PPD), LLC.

9.1.3 Measurement of Circulating Cytokines in Human Plasma

Multiplex cytokine measurements will be carried out in isolated human plasma samples from patients before and after therapy using the Meso Scale Discovery (MSD) multiplex cytokine assay and electrochemiluminescence platform. Specifically, we will evaluate up to 10 pro-inflammatory and Th1/Th2 immune mediators (IFN- γ , IL-1b, IL-2, IL-4, IL-6, IL-8, IL-10, IL-12p70, IL-13, and TNF- α) using the validated MSD V-Plex Human Pro-Inflammatory Cytokine Panel. Quality control samples with pre-defined levels of each cytokine will be used to verify assay performance. The Immune Monitoring Facility at MSKCC is equipped with the MSD QuickPlex SQ 120 Imager for detection and quantitation of ECL signals from this assay, and has extensive experience running cytokine immunoassays in human biological fluid samples.

9.1.3.1 *Collection of Specimen(s)*

Plasma used for this assay will be obtained from the plasma supernatant of the PBMC density gradient spins, from section 9.1.4.1 below.

9.1.3.2 *Handling of Specimens(s)*

The samples should be labeled with the PBTC Accession number and the Course, Day information for each sample.

9.1.3.3 *Shipping of Specimens*

The sample collection and shipping dates must be documented in the eCRF. All samples should be forwarded via FedEx, Monday through Thursday, by completing the internet form at <http://www.fedex.com/us/> and requesting FedEx to email the laboratory. Fed Ex account information for the shipment of samples can be obtained on the PBTC website. Weekend deliveries are not permitted. Sites should contact the PBTC CRB of shipment. Biologic specimens should be shipped on dry ice, along with a completed Biologic Specimen Transmittal Form located on the PBTC-051 webpage to PBTC CRB as described in section 9.1.1.2.

9.1.3.4 *Site Performing Correlative Study*

Immune Monitoring Facility, Memorial Sloan Kettering Cancer Center

9.1.4 Characterization of T Cell Activation/Exhaustion Phenotype in Human PBMC

Multiparameter flow cytometry will be utilized to characterize T cell subset frequencies and the expression of a number of surface and intracellular markers of T cell activation and exhaustion. Specifically, a validated 11-color flow panel will be used to quantitate live, conventional and regulatory T cells as defined by CD3, CD4, CD8, and FoxP3 markers. Gated cell subsets will then be evaluated for expression of proliferative/costimulatory markers including Ki-67 and ICOS, as well as T cell exhaustion/inhibitory molecules such as CTLA-4, PD-1, TIM-3, and LAG-3. Marker positivity will be defined using the appropriate gating controls. The Immune Monitoring Facility at MSKCC is equipped with the BD Fortessa 4-laser flow cytometer for acquisition and analysis of cells stained with the flow panels in the core.

9.1.4.1 Collection of PBMC and Plasma Specimen(s) (for T cell phenotyping and Cytokine analysis respectively)

The blood samples (minimal 16 mL, ideal 32 mL) will be collected pre-treatment and 1-week post-the first dose of APX005M. Additional blood samples should be collected at 2 weeks, 3 weeks, 6 weeks, and 9 weeks post-treatment if feasible.

Collection and Processing of PBMC and Plasma Using CPT tube

- Peripheral blood should be collected in a BD Vacutainer CPT™ Cell Preparation Tube with Sodium Heparin. 8 mL CPT tubes can be obtained from Fisher Scientific (Cat# 14-959-51D) or Becton-Dickinson (BD No. 362753). The 8 mL tubes have a 6 mL minimum draw. Samples should ideally be processed within 2-4 hours of collection. In the event of a delay in processing, samples can be left at ambient temperature for up to 24 hours before processing preferably with gentle rotation to keep the anticoagulant in the tube mixed with the blood.
- Centrifuge the CPT™ tube at 1500 x g for 30 minutes at room temperature (20° C to 25° C). DO NOT APPLY THE BRAKE ON THE CENTRIFUGE. Set brake to 0 (“slow mode”).
- It may be necessary to spin the tube 10-15 min longer to ensure that all of the red blood cell components have been separated from the plasma layer through the polyester gel barrier if separation does not occur during initial spin.
- The tube should be removed immediately from the centrifuge. The white mononuclear cell layer and yellow plasma lie above the polyester gel plug.
- Using a sterile pipette, remove as much of the plasma component (upper half of the CPT tube) without disturbing the mononuclear cell layer. Save plasma supernatant for cytokine analyses described in section 9.1.3 by distributing 0.5 mL aliquots into 1 mL cryovials and freezing at -20°C to -80°C.
- Transfer the mononuclear cell layer to a labeled 15-mL conical centrifuge tube and add sufficient sterile room temperature magnesium or calcium-free phosphate buffered saline (PBS) containing 10% heat-inactivated fetal bovine serum (FBS) to fill the conical tube to 15 ml and recap.
- Centrifuge at 450 x g for 10 minutes in a refrigerated centrifuge (4°C). Use acceleration 9, with brakes on (“fast mode”).
- Remove supernatant, being careful not to aspirate the cellular pellet at the bottom of the tube.
- Resuspend cells into a total of 15 mL fresh PBS/10% FBS wash buffer and centrifuge again at 300 x g for 10 min at 4°C. Use acceleration 9, brakes on (“fast mode”).
- Resuspend cells in 5-10 mL fresh wash buffer and place on ice.
- Remove 10 µl of the cell suspension and dilute in appropriate buffer for counting cells using a hemacytometer or automated cell counting instrument.
- Count cells, taking into account dilution factor, and record total yield and viability.
- Centrifuge cell sample at 250 x g 4°C, brakes on, for 10 minutes.
- Remove supernatant and resuspend cells at 6-8 x 10⁶ viable cells/mL in ice-cold cell freezing media (FBS containing 10% DMSO) and aliquot 1 mL into labeled cryovials for each sample.
 - NOTE: For a total cell count below 6 x 10⁶ viable cells, resuspend sample in a

minimum of 0.5 ml in 1 cryovial.

- Place cryovials in a [name] or CoolCell -1°C/min controlled rate freezing container and place cooling container at -80°C for at least 24 hrs for controlled rate freezing.
- Transfer cells in cryovials to a liquid nitrogen freezer within a week of the initial -80°C freezing.

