3.1.3 Age

Patient must be ≥ 1 and ≤ 21 years of age at the time of enrollment.

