3.1.9 Organ Function

Patients must have adequate organ and bone marrow function as defined below:

- Absolute Neutrophil Count (ANC) ≥ 1.0 x 10⁹ cells/ L
- Platelets ≥ 100 x 10⁹ cells/L (unsupported, defined as no platelet transfusion within 7 days)
- Hemoglobin ≥ 8 g/dL (may receive transfusions)
- Total bilirubin ≤ 1.5 times institutional upper limit of normal (ULN)
- AST(SGOT)/ALT(SGPT) ≤ 3 x institutional upper limit of normal (ULN)
- Albumin ≥ 3 g/dl
- Serum creatinine based on age/gender as noted in Table 1. Patients that do not meet the criteria in Table 1 but have a 24 hour Creatinine Clearance or GFR (radioisotope or iothalamate) ≥ 70 mL/min/1.73 m² are eligible.

Table 1

Serum Creatinine for age/gender		
Age	Maximum Serum Creatinine (mg/dL)	
	Male	Female
1 to < 2 years	0.6	0.6
2 to < 6 years	0.8	0.8
6 to < 10 years	1	1
10 to < 13 years	1.2	1.2
13 to < 16 years	1.5	1.4
≥ 16 years	1.7	1.4

The threshold creatinine values in this Table were derived from the Schwartz formula for estimating GFR (Schwartz et al. J. Peds, 106:522, 1985) utilizing child length and stature data published by the CDC.

- Cardiac Function:
 - Left Ventricular Ejection Fraction (LVEF) > 50%
 - ECG QTc ≤ 450 msec
- Pulmonary Function:
 - Oxygen saturation as measured by pulse oximetry is > 93% on room air and no evidence of dyspnea at rest

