5.1.3 Criteria to Start Subsequent Courses

A course may be repeated every 3 weeks if the patient has at least stable disease, all drug-related toxicities return to baseline or \leq Grade 1 (excluding alopecia and Grade 2 fatigue) and has again met laboratory parameters as defined in Section 3.1.9. If a patient does not meet these parameters at the end of the treatment course then APX005M should be held until parameters meet the eligibility criteria.

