
A. To be completed prior to each course.
 
B. To be done more frequently throughout the duration of treatment if required to monitor toxicities.
 
C. Within 72 hours prior to starting treatment, if eligibility pregnancy test is within 72 hours, no need to repeat prior to Course 1.
 
D. Coagulation tests include PT, INR, and aPTT; INR is only required at screening and as clinically indicated thereafter.
 
E. Patients will have MRI Brain with and without contrast performed within 3 weeks prior to enrollment, at the end of course 2, every 3 courses through course 14, and then every 4 courses till the end of therapy, and at the time of disease progression or completion of treatment.
 
F. All the correlative studies are required. See section 9.1 for collection schedule and sample requirements.
 
G. Cerebrospinal fluid assessment via lumbar puncture or Ommaya tap for patients with clinical concern for disseminated disease per the discretion of the treating physician.
 
H. B cell count will be tested pre-therapy, at the end of course 2, every 3 courses through course 14, and then every 4 courses till the end of therapy, and at the time of disease progression or completion of treatment.
 
I. Spine MRI should be performed prior to therapy and at the same time points as standard Brain MRI, if clinically indicated.
 
J. CD4 cell count should be tested pre-therapy for patients with history of autologous bone marrow/stem cell transplant.
				

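### The required PBMC/cytokine blood volume is fixed from age 1, with no weight scaling or research-blood limit; minimum firm sampling takes about 7–10% of an assumed 10 kg child's blood volume by day 42

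*Combined protocol and SAP*

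**What the plan says.** On volume and timing, section 9.1.4.1 states: "The blood samples (minimal 16 mL, ideal 32 mL) will be collected pre-treatment and 1-week post-the first dose of APX005M". It then adds: "Additional blood samples should be collected at 2 weeks, 3 weeks, 6 weeks, and 9 weeks post-treatment if feasible". So two draws are firm and four are conditional. On tubes it says: "The 8 mL tubes have a 6 mL minimum draw"; no smaller tube is named there, although section 9.1.1.2 lists a 4 mL tube for repository samples.

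The section 9 table repeats the 16 and 32 mL figures and marks both assays as required. Footnote F of the study calendar agrees: "All the correlative studies are required". The one rule for scarce blood, under the section 9 table, puts PK and ADA first. It ranks assays and does not cap volume.

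Section 3.1.3 sets the age range: "Patient must be ≥ 1 and ≤ 21 years of age at the time of enrollment". No minimum weight is given. Section 3.1.9 requires hemoglobin of at least 8 g/dL and allows transfusion. Section 5.1.3 permits a further course only if the patient "has again met laboratory parameters as defined in Section 3.1.9"; otherwise APX005M is held.

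**The concern.** The PBMC/cytokine sample is the largest research draw in the trial, and it is the same for a 1-year-old as for a 21-year-old. Elsewhere the protocol does allow for small patients: section 8.3.2 has a separate drug-preparation step below 40 kg.

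The first issue is avoidable blood loss in the smallest children. The second is interpretation. Anemia is a listed APX005M effect (section 7.1.1). Grade 1–2 events are recorded only if at least possibly related to the drug (section 7), and toxicity is summarized by attribution (section 13.3). If research blood volume is not recorded, whoever attributes a fall in hemoglobin, or a course held under section 5.1.3, lacks a relevant fact.

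**Working it through.** The documents give no total research volume or percentage, so there is no stated figure to reproduce.

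**Inputs from the protocol**
- PBMC/cytokines (9.1.4.1): 16 or 32 mL per draw; 2 firm draws, 6 if all are taken.
- PK (9.1.2.1): 2 mL at 5 + 5 + 2 + 2 = 14 time points over courses 1–4.
- ADA, 2 mL. Reading A (9.1.2.1): before dosing in each of courses 1–4. Reading B (9.1.2.2, taken literally): a PK tube and an ADA tube, 4 mL together, at every time point.
- Sequencing for tumor mutational burden (TMB, 9.1.5): 5 mL once, or 0 if taken from the PBMC tubes, since 9.1.5.1 refers back to 9.1.4.1.

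**Assumptions not in the documents:** weight 10 kg; blood volume 75–80 mL/kg, so 750–800 mL. Weekly safety blood is left out, and so is red-cell regeneration.

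**Formulas**
- Total = draws × volume + PK/ADA + (0 or 5) mL.
- Share = total ÷ (weight × mL/kg).

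**PK/ADA subtotals**
- Day 8: A, 5×2 + 1×2 = 12 mL; B, 5×4 = 20 mL.
- Day 42: A, 10×2 + 2×2 = 24 mL; B, 10×4 = 40 mL.
- Week 9: A, 14×2 + 4×2 = 36 mL; B, 14×4 = 56 mL.

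In the table, the low end is reading A without the 5 mL at 80 mL/kg. The high end is reading B with the 5 mL at 75 mL/kg. The single-draw rows count PBMC/cytokine blood only.

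| Scenario | mL | 10 kg | 20 kg |
|---|---|---|---|
| One draw, 16 mL | 16 | 2.0–2.1% | 1.0–1.1% |
| One draw, 32 mL | 32 | 4.0–4.3% | 2.0–2.1% |
| Day 8, 2 firm draws at 16 mL | 44–57 | 5.5–7.6% | 2.8–3.8% |
| Day 42, 2 firm draws at 16 mL | 56–77 | 7.0–10.3% | 3.5–5.1% |
| Day 42, 2 firm draws at 32 mL | 88–109 | 11.0–14.5% | 5.5–7.3% |
| Week 9, 2 firm draws at 16 mL | 68–93 | 8.5–12.4% | 4.3–6.2% |
| Week 9, 6 draws at 16 mL | 132–157 | 16.5–20.9% | 8.3–10.5% |
| Week 9, 6 draws at 32 mL | 228–253 | 28.5–33.7% | 14.3–16.9% |

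Example, day 42 at the minimum: low 32 + 24 = 56 mL, 56/800 = 7.0%; high 32 + 40 + 5 = 77 mL, 77/750 = 10.3%. At 8 kg the same row is 56/640 to 77/600, or 8.8–12.8%; at 12 kg it is 56/960 to 77/900, or 5.8–8.6%.

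**Hemoglobin.** With simple proportional dilution and no regeneration, the starting value that falls to 8 g/dL is 8/(1 − share). For a 7% loss this is 8/0.93 = 8.6 g/dL; for 10% it is 8/0.90 = 8.9 g/dL. A child starting at 10 g/dL who loses 10% reaches 9.0 g/dL, still above the limit. The re-dosing question therefore arises mainly for children who start near 8–9 g/dL.

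**The case against.** Much can be said for the plan as written. Four of the six draws depend on feasibility, PK and ADA already have priority, and 9.1.4.1 accepts low cell counts. The assays serve exploratory objectives. Stratum 1 has finished accruing, and Stratum 2 plans about 12 evaluable patients; nothing shows how many will weigh near 10 kg. Sites may apply local limits, and the consent pages were not available here, so a limit stated there cannot be excluded.

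These points narrow the reach but do not supply the missing rule. Neither the feasibility wording nor the assay priority limits the two firm draws by weight.

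A reader might also infer that research sampling distorts the primary safety endpoint. The documents do not support that. Transfusion is allowed (3.1.9). Anemia is absent from Table 3. As a hematologic DLT in itself, only grade 4 anemia counts (5.2.1.2). The other routes in 5.2.1 need an event related to APX005M that leads to dose reduction, permanent cessation or a delay of more than 2 weeks. Attribution includes unlikely and unrelated categories (7.2.2), and blood counts are weekly in courses 1–2. Phlebotomy anemia short of grade 4 would enter the DLT count only if misattributed. That is possible, but not shown.

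**Conclusion.** The concern holds in a limited form. A required volume is fixed for all ages from 1 year, with no scaling to weight and no per-draw or cumulative ceiling in the available text. For an assumed 10 kg child, minimum firm sampling costs about 7–10% of blood volume within the 42-day dose-finding period, and about half that at 20 kg.

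It would be wrong to read the figure of about 30% as the required burden or as the size of one draw. It is a nine-week cumulative total that needs the ideal volume at all six draws, four of them conditional, and it takes no account of regeneration. All shares rest on the assumed weight and mL/kg.

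The consequence is an avoidable burden on the smallest children, with possible difficulty in attributing anemia or a held course in those starting near 8–9 g/dL. This is a cheap improvement, not a defect in the dose-finding design.

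**What to change.** For patients still to be enrolled or sampled:

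- In 9.1.4.1 and the section 9 table, replace the fixed minimum with a volume scaled to weight. Add a ceiling per draw and per rolling period, set to the participating institutions' pediatric research-blood limit and counting all study blood.
- State the order in which samples are dropped: the conditional PBMC draws first, PK and ADA last.
- Take the TMB cells from the PBMC tubes already drawn, as the cross-reference in 9.1.5.1 suggests.
- Reconcile 9.1.2.1 with 9.1.2.2 on whether an ADA tube is drawn at every PK time point. Through week 9 the two readings differ by 56 − 36 = 20 mL.
- Record research blood volume so that it is available when anemia is attributed.

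The cost is protocol and laboratory-manual wording and one recorded item. The downside is fewer cells from the smallest children, which 9.1.4.1 already accommodates by placing low-count samples in a single cryovial.

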9.1.4.2 Handling of Specimens(s)

The samples should be labeled with the PBTC Accession number, sample type, date of collection and study ID for each sample.

9.1.4.3 Shipping of Specimens

The sample collection and shipping dates must be documented in the eCRF. All samples should be forwarded via FedEx, Monday through Thursday, by completing the internet form at <http://www.fedex.com/us/> and requesting FedEx to email the laboratory. Fed Ex account information for the shipment of samples can be obtained on the PBTC website. Weekend deliveries are not permitted. Sites should contact the PBTC CRB for shipment, and specimens will be shipped to PBTC CRB. Biologic specimens should be shipped on dry ice, along with a completed Biologic Specimen Transmittal Form located on the PBTC-051 webpage to PBTC CRB as described in section 9.1.1.2.

9.1.4.4 Site Performing Correlative Study

Immune Monitoring Facility, Memorial Sloan Kettering Cancer Center

9.1.5 Tumor mutational burden assessment

Pre-trial frozen or FFPE tumor tissue (10-20 unstained slides) and PBMC (from 5 mL blood) will be submitted. We will perform whole exome sequencing on matched tumor and normal PBMC pairs. We will also perform RNAseq and TCR sequencing. We will analyze this data to determine how mutational burden, spectrum of neoantigens, and TCR repertoires influence patient response. We have pioneered these approaches for immunotherapeutics and will apply the expertise to dissecting the genomic and immunologic correlates of response versus resistance.

For DIPG patients without tumor samples, we will perform peripheral TCRseq analysis, which just requires PBMCs.

9.1.5.1 Collection of Specimen(s)

Frozen or FFPE samples will be obtained for tumor genomics analysis. Tumor samples should be collected and delivered to PBTC CRB. PBMCs should be collected as described in section 9.1.4.1 above.

9.1.5.2 Handling of Specimens(s)

The pre-treatment tumor tissue and PBMC should be labeled with the PBTC Accession number, sample type, date of collection and study ID.

9.1.5.3 *Shipping of Specimen(s)*

The sample collection and shipping dates must be documented in the eCRF. All samples should be forwarded via FedEx, Monday through Thursday, by completing the internet form at <http://www.fedex.com/us/> and requesting FedEx to email the laboratory. Fed Ex account information for the shipment of samples can be obtained on the PBTC website. Weekend deliveries are not permitted. Sites should contact the PBTC CRB for shipment. Biologic specimens should be shipped in dry ice (for frozen tumor samples) or at room temperature (for FFPE blocks), along with a completed Biologic Specimen Transmittal Form located on the PBTC-051 webpage to PBTC CRB as described in section 9.1.1.2.

9.1.5.4 *Site Performing Correlative Study*

Immunogenomics and Precision Oncology Platform, Memorial Sloan Kettering Cancer Center.

9.2 **Neuroimaging Studies**

Patients will have MRI Brain with and without contrast performed within 3 weeks prior to enrollment, at the end of course 2, every 3 courses through course 14, and then every 4 courses till the end of therapy, and at the time of disease progression or completion of treatment. MRI Spine should be performed prior to therapy and at the same time points as standard MRI Brain, if clinically indicated. Tumor response will be determined for all subjects by comparison of the product of 2-dimensional measures of the tumor on the baseline and follow-up MRI scans using T-2 and/or FLAIR sequences. Due to concern regarding immune-related pseudoprogression, in the absence of clinical deterioration, any initial assessment of progressive disease (PD) will be confirmed by a repeat evaluation at the next tumor assessment time point, but no sooner than 4 weeks later.

Standard MR imaging will include Sagittal T1 MPRAGE, axial T2 FLAIR, axial T2, and post gadolinium sagittal T1 MPRAGE (with reconstructions). The standard MR parameters are listed on the PBTC NIC web page located at <http://www.childrenshospital.org/research/centers-departmental-programs/pediatric-brain-tumor-consortium-neuroimaging-center> under Neuroimaging Studies/ Specific MR Imaging Sequences- Open PBTC Protocols. There is also a link to the same PBTC-NIC webpage from the PBTC-051 protocol study page.

Volumetric analyses will be done at the Neuroimaging Center (NIC, Children's Hospital Boston) via the Vitrea (Vitrea™) workstation, from the axial FLAIR and T1-weighted post-contrast brain images.

9.2.1 **Image Transfer**

For those patients showing a response, the MRI scan from that date, the confirmation scan obtained approximately 3 courses later, if available and the corresponding baseline scan should be uploaded to the PBTC Neuroimaging Center (NIC) for central review.

All patient specific data are stripped from the images and replaced with PBTC Accession numbers prior to transmitting the images to the NIC. All image data transfer is accomplished using PGP (pretty-good-privacy) 128-bit encryption which meets industry standard for secure communication.

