5.4.2 Off Treatment Criteria

At the discontinuation of treatment, the “Off Treatment Date” is to be recorded in the eCRF and is to be consistent with the reason given for going off treatment. The “Last Treatment Date” is defined as the last date that the patient received protocol based therapy. Date of “off treatment” must be the greatest of the date of last treatment, date of procedure, date of patient assessment, notification of patient/family decision, or decision made by the physician that resulted in the patient being taken off protocol treatment. The reason for discontinuation of treatment must be documented by the attending investigator in the medical record and recorded in the eCRF.

Patients will be considered Off Treatment for the following reasons:

- Development of unacceptable toxicity as outlined in section 5.2.1. See section 7 for specific reporting requirements.
- Progressive disease (PD) as described in section 11.3.
- Development of a medical or psychiatric illness that in the investigator's judgment renders the patient incapable of further therapy on this protocol or the treating physician determines continuation on this study is not in the patient's best interest.
- The patient, parent or legal guardian refuses further treatment on this protocol. In this case the investigator should clarify if the family also wishes to withdraw consent for continued participation for data collection purposes.
- Completion of all protocol defined treatment
- Pregnancy
- Non Compliance that in the opinion of the investigator does not allow for ongoing participation.

Patients who are off protocol therapy must be followed until an “Off Study Criterion” is met.

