11.3.4 Progressive Disease (PD)

Progressive Disease (PD): Progressive neurologic abnormalities or worsening neurologic status not explained by causes unrelated to tumor progression (e.g., anticonvulsant or corticosteroid toxicity wean, electrolyte disturbances, sepsis, hyperglycemia, etc.), OR a greater than 25% increase in the bi-dimensional measurement, taking as a reference the smallest disease measurement recorded since the start of protocol therapy, OR the appearance of a new tumor lesion.

Increasing doses of corticosteroids required to maintain stable neurological status should be strongly considered as a sign of clinical progression unless in the context of recent wean or transient neurologic change.

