*** Consideration for possible pseudo-progression**

For patients showing possible radiographic evidence of tumor progression on MRI during the first 6 months after initiation of APX005M (on required MRI studies performed at the end of Course 2, 5, 8), the treating physician will have the option of allowing the patient to remain on study, continuing protocol therapy, and repeating disease reassessment in 4-6 weeks. Provided that the patient does not show clinical deterioration consistent with tumor progression, has been on a stable or declining dose of steroids, and the subsequent MRI demonstrates tumor regression or stable disease, then the patient will remain on study and continue protocol therapy, and the frequency of subsequent MRI will revert to pre-specified intervals. If the repeat MRI after 4-6 weeks shows disease progression, rather than pseudo-progression, then the time of progression will be the date of the initial MRI, not the follow up scan. The addition of steroids is allowed, at the time of suspected pseudo-progression, as long as the patient can be maintained on a decreasing dose.

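### Two pairs of rules conflict: Sections 5.4.3 and 5.4.4 end DIPG follow-up at different times, and Sections 9.2 and 11.3.4 differ on whether radiographic progression must be confirmed

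*Combined protocol and SAP*

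**What the plan says.** **Follow-up of DIPG patients.** Section 5.4.3 keeps Stratum 2 patients in long-term follow-up for three years counted from treatment start, with quarterly data on progression, survival and related adverse events. Section 5.4.4 lists completion of that follow-up as one way off study. The last item of the same list ends follow-up of Stratum 2 patients removed from treatment (other than by death or withdrawn consent) at death or three years after diagnosis, whichever comes first. Section 5.4.5 then stops collection of disease status, with an exception for adverse events at least possibly related to the agent. Section 11.3.5 counts PFS from treatment start. Section 11.3 gives no origin for OS.

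**Confirmation of progression.** Section 9.2, citing immune-related pseudo-progression, says that without clinical deterioration an initial reading of "progressive disease (PD) will be confirmed by a repeat evaluation at the next tumor assessment time point, but no sooner than 4 weeks later". It sets no end to the period in which this applies. Section 11.3.4 accepts "a greater than 25% increase in the bi-dimensional measurement" as PD, with no confirming scan. Its pseudo-progression note covers the first six months only: for scans "at the end of Course 2, 5, 8), the treating physician will have the option of allowing the patient to remain on study". Under that option, drug goes on and imaging is done again four to six weeks later. The patient then counts as not progressed only if the repeat shows regression or stable disease, there is no clinical deterioration, and steroids have been stable or falling. If the repeat shows progression, "then the time of progression will be the date of the initial MRI, not the follow up scan".

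**The concern.** Response, response duration, PFS and OS in DIPG are the secondary objective (Section 1.2). Each time-to-event summary needs one event rule and one follow-up period, and the protocol gives two of each.

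The whichever-comes-first phrase in 5.4.4 does not settle the follow-up question. It chooses between death and three years from diagnosis, not between the two clocks. A site applying 5.4.4 would stop recording disease status while 5.4.3 still asks for it.

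For progression, the same scans could be counted as an event under one section and as unconfirmed under the other. At stake are the tail of the PFS and OS curves and the event status of some PFS and response-duration records.

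**Working it through.** **Follow-up clock.** Inputs: enrollment 6 to 14 weeks after the end of radiotherapy (Section 3.1.1); first dose within 7 days of enrollment (Section 3.4); 4.348 weeks per month.

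- End of radiotherapy to first dose: 6 + 0 = 6 weeks at the shortest, 14 + 1 = 15 weeks at the longest.
- Diagnosis precedes radiotherapy, so three years from diagnosis always falls before three years from first dose, by at least this interval.
- Minimum loss: 6 / 4.348 = 1.38 months and 15 / 4.348 = 3.45 months (3.4497, so 3.4 to one decimal).
- Follow-up left after first dose, at most: 36 − 1.38 = 34.6 months and 36 − 3.45 = 32.6 months (32.55).

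The time from diagnosis to the end of radiotherapy adds to the loss, but the documents do not give it. Assuming 0 to 4 weeks before radiotherapy and 5 to 7 weeks of radiotherapy, the loss is 6 + 5 + 0 = 11 weeks to 15 + 7 + 4 = 26 weeks, or 11 / 4.348 = 2.5 months to 26 / 4.348 = 6.0 months.

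**Progression.** No arithmetic applies, so the rules are set side by side for radiographic PD without evident clinical deterioration.

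| Case | Section 11.3 | Section 9.2 | Agree? |
|---|---|---|---|
| Confirmed on repeat | Event; 11.3.5 takes the earliest date | Event | Yes |
| Course 2, 5 or 8; refuted; steroids stable or falling | Pseudo-progression, not an event | Unconfirmed | Yes |
| Course 2, 5 or 8; refuted on imaging; steroids rose | Conditions of the note not met, so PD stands | Unconfirmed; no steroid condition | Can differ |
| First seen at Course 11 or later; refuted | Event; no repeat option | Unconfirmed | Differ |
| Never re-imaged | Event | Unconfirmed; does not say how to count it | Differ |

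The third case is worded as can differ because 11.3.4 also says a rising steroid requirement should be strongly considered a sign of clinical progression. If the site judges it so, the 9.2 condition fails and the sections agree.

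**The case against.** **Section 11.3 governs.** The off-treatment rule in 5.4.2 lists "Progressive disease (PD) as described in section 11.3", 11.3.5 takes the earliest documentation of PD, and the pseudo-progression note is the specific rule inside the response criteria. This is the better reading of the text and it stands in part. But 9.2 is worded as a requirement, and nothing makes it subordinate. Its clinical-deterioration condition does not reconcile the two, because the note in 11.3.4 covers the same radiographic-only situation.

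**The intervals may be compatible.** If the next assessment in 9.2 meant a scheduled scan, the repeat after Courses 2, 5 and 8 would come 9 weeks later rather than at 4 to 6. But the four-week floor in 9.2 matches the lower end of 4 to 6 weeks and would do no work if only scheduled scans counted, since those are all at least 6 weeks apart. The interval is not counted here as a further conflict.

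**Stronger readings that a reader might infer, and that the documents do not support:**

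- *Conflicting treatment instructions from Course 11 on.* Section 9.2 says nothing about dosing. Dosing is set by 5.4.2 and by 5.1.3 ("A course may be repeated every 3 weeks if the patient has at least stable disease"). Stopping drug and re-imaging at least four weeks later are compatible, so no count of extra doses follows.
- *Loss of late-toxicity data.* The adverse events that 5.4.3 asks for in long-term follow-up are those at least possibly related to the agent. Section 5.4.5 exempts the same class from its stop. What shortens is active quarterly contact.
- *A child stopped at once is necessarily never re-imaged.* The calendar has no further scheduled scan after treatment ends for progression, but 5.4.3 still collects dates and results of progression assessments off treatment.

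**Conclusion.** Both conflicts hold, and both are minor. The follow-up conflict costs at least 1.4 to 3.4 months of progression and survival follow-up, on document figures alone. The 2.5 to 6.0 month range rests on assumed radiotherapy timing. It affects only DIPG patients still alive near three years, among about 12 evaluable patients planned (Section 13.1.3).

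The progression conflict changes event status only in the three cases where the sections do not agree. The documents give no rate of refuted or never-repeated PD, so the number affected is unknown and no shift in PFS is claimed. It does not touch OS.

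Section 13.3 reports these endpoints descriptively and treats all of these analyses as exploratory. Dose decisions rest on DLTs (Section 13.1), so neither conflict affects the MTD or the Stratum 2 dose rule.

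**What to change.** 1. In 5.4.4, replace the diagnosis clock with three years from the start of protocol treatment, as in 5.4.3 and consistent with the PFS origin. State the same origin for OS.
2. State one rule in 11.3.4 and 11.3.5, apply it by reference to response duration in 11.3.6, and make 9.2 refer to it. Radiographic PD is an event dated to the first scan if it is confirmed at least four weeks later or never re-imaged. It is not an event only if the repeat refutes it with no clinical deterioration and with stable or declining steroids.
3. Have the sponsor set one time window for both sections. Add a sensitivity analysis for never-re-imaged cases.

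The cost is small. The event rule keeps the present 11.3.4 default for PD never re-imaged and could go in an analysis note before reporting. Progression-assessment results are already collected under 5.4.3, and steroid use is recorded under 5.3.1. The off-treatment list in 5.4.3 does not name steroid dose, so a repeat scan done off treatment would need it requested alongside. The clock and the alignment of 9.2 need a short amendment, which is practical while Stratum 2 is accruing (Section 5.1.1). The clock change adds at least 1.4 to 3.4 months of quarterly contact for the long survivors.
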